13.1 Serious Adverse Event (SAE)

Any untoward medical occurrence that:

- have caused the patient's death,
- is life-threatening,
- requires inpatient hospitalization or prolongation of existing hospitalization,
- results in persistent or significant disability/incapacity,
- is qualified as another medically significant event or condition

- will be classified as serious.

13.2 Criteria to be evaluated by the investigator (1st assessment)

Special attention is to be paid to the occurrence of SAE throughout every stage of the clinical trial. The GP and subsequently the PI should evaluate all events according to the criteria and steps mentioned below.

13.2.1 Assessment of intensity

Any observed SAE has to be graded regarding its intensity.	
MILD	Does not interfere with patient's usual function, easily tolerated.
MODERATE	Interferes to some extent with patient's usual function.
SEVERE	Interferes significantly with patient's usual function, incapacitating with inability to work or carry out usual activity.

13.2.1 Assessment of causality

Decision as to whether the intervention (narrative therapy and improved treatment-as-usual) is causally related to the SAE is determined by evaluation of all accessible data (classification: suspected; not suspected).

When the final causality assessment is unknown and it is uncertain whether or not the investigational therapy caused the event, then the event should be handled as an SAE related (suspected) to the investigational therapy for reporting purposes.

13.3 Risk benefit Assessment

The only potential SAE is the possibility of triggering a severe depression, psychosis, an episode or a secondary hypochondriacally disorder by frequent interrogation of disease symptoms. The same applies to signs of acute suicidal behavior. After consultation with the principal investigator and the DSMB, inpatient treatment centers are available for both indications.

13.4 Criteria to be evaluated by the Data and Safety Monitoring Board (2nd assessment)

In addition to the first evaluation of any serious adverse event that is performed by the PI, a second evaluation with respect to seriousness, causality and expectedness and a risk-benefit assessment is performed at the investigator's discretion by the DSMB to process safety evaluation according to a four-eyes principle.

13.5 Documentation and Reporting of Serious Adverse Events

Any SAE has to be reported immediately to the PI.

Documentation and evaluation of each SAE occurring:

- after the subject has been randomized and has received intervention
- up to the end of trial at T2

13.5.1 Initial reporting of SAE

SAE shall be reported using a report form with the following information (see appendix):

Report SAE to the Principal Investigator
[name]. med. [name]
IMMEDIATELY
after becoming aware of this event
[contact]

13.5.2 Reporting to the ethics committee

The DSMB will be informed on a regular basis. If a relationship between the intervention and the SAE cannot be ruled out, the PI will report the event to the ethics committee including following information:

- A full description of the event(s)
- Trial Site
- Severity
- Criteria for regarding the event as serious
- Description of specific symptoms
- Description of specific diagnosis.

All SAEs will be followed up and a follow-up report as well as a closing report will be sent to the ethics committee by the investigator.

14 Safety and Quality management

To reduce the risk of inefficient clinical management (i.e. exposition), GPs will be trained in accordance to GCP- and S3-Guidelines in their ability to care for patients with PTSD and to detect and deal with SAE appropriately. GPs will be trained to prompt immediate referral to specialist care (clinical pathway or trial back-up clinic) in case of SAE (i.e. of symptom deterioration). Clinical checklists will aid in detection of and reporting of deterioration in symptoms. Departments of Psychiatry in Munich, Berlin, Hamburg, Dresden and Tübingen have guaranteed to provide priority access to mental health services and psychiatric emergency treatment.

Similarly, telephone interviewers collecting data at T1 and T2 will be trained in detecting indications of SAE. All instructions and processes related to any interaction with the patient (face-

to-face or per telephone), to detection and handling of SAE and to handling of data will be described additionally accordingly as standard operating procedures (SOPs) for all staff involved.

14.1 Data Safety and Monitoring Board

An independent Data and Safety Monitoring Board (DSMB) has been installed. The DSMB will monitor recruitment, feasibility, the integrity of the trial, safety of study participants, and will review recruitment rates and accumulating safety summaries on a regular basis; additional data may be requested during the conduct of the trial. A DSMB *Charter* will outline the roles and responsibilities of its members. The DSMB may recommend discontinuation of the trial or modification of the protocol for safety reasons at any time during the trial

Particular attention will be paid to the incidence of particular SAE reported during the trial period, including death, suicidal behaviour, “severe intrusions”, clinically significant intervention-related symptom deterioration, and referral to psychiatric care (e.g. psychiatric back-up centres located at the Departments of Psychiatry) or hospitalization.

14.2 Safety Assessment

Patient’s safety will be monitored regularly by the GP between T0 and T2. Safety issues will be reported for all participants during their appointment at the GP’s office (3 sessions S1 to S3 in the intervention group; 3 visits between T0 and T1 in the iTAU group). The monitoring form consists of 15 items assisting the GP in assessing the patients’ current state of health with regard to detection of SAE. Scoring of the various items assessed by a coloring code (red, yellow, green) allows the GP to identify single issues that may be suspected for SAE as well as providing the GP with an overall impression of the patients state of health enabling the GP to respond appropriately, should the patient show signs of mental deterioration. Safety data will subsequently be stored in the patient’s medical record and in the CRF (paper-and-pencil format).

14.2.1 Early termination of the trial by the patient

A patient may withdraw their consent to participate in the study at any time without giving reasons. In such a case the patient is asked to name a possible withdrawal reason, but there is no obligation to do so. Time and reasons for withdrawal (if known) will be documented in the CRF. By discontinuing the study, the patient does not suffer any disadvantages for further treatment.

14.2.2 Exclusion of a patient from the trial

Patients can be excluded from the study if a breach of the inclusion or exclusion criteria is post-hoc detected. In the case the family physician terminates the participation in the trial his/her patient will be excluded from the study as well.

Data from patients who drop out of the study after randomization, either through withdrawal or exclusion, are included in an intention-to-treat (ITT) analysis.

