### 3 Trial Objectives and Endpoints

The overall goal of the PICTURE trial is to evaluate whether a primary care based NET-oriented intervention improves patient-reported outcomes such as PDS total severity score, quality of life, common co-morbidities depression and anxiety in patients with PTSD after ICU discharge. This study aims to describe and compare the real-world effectiveness safety and applicability of a primary care based complex psychological intervention with improved "usual care".

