#### 8.4 Definition of populations included in the analyses

This clinical trial will be analyzed according to the ITT principle. This means that the subjects will be analyzed in the treatment arms to which they were randomized, irrespective of whether they refused or discontinued the treatment, or whether other protocol violations are revealed.

The per-protocol (PP) population is a subset of the ITT population.

An analysis per-protocol (PP) will exclude or censor endpoint information considering major protocol deviations potentially effecting subjects' specific endpoint value, e.g., in the case of major violation of eligibility criteria (patient or GP level), lack of sufficient treatment per protocol (e.g., predefined number of sessions or consultations between T0 and T1) or unsatisfactory evaluations for endpoint assessment at predefined time points (telephone survey). The PP analyses excluding data from protocol non-adherers will be performed for the purpose of a sensitivity analysis and investigating robustness of results.

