19.2 Premature Termination of the Trial for Individual Subjects

If the clinical trial is prematurely terminated or suspended for any reason, the investigator should promptly inform the subjects and ensure appropriate therapy and follow-up.

There are different grades of deviations from the study flow ranging from minor, major protocol violations, (such as delayed or unscheduled (telephone) visits, discontinuation of intervention, taking medication listed under prohibited therapy / concomitant medication (see protocol violations section 15.5) to complete withdrawal. Complete withdrawal should be a rare exception.

Whenever a subject is withdrawn totally from the trial, a complete final examination as scheduled for the premature termination/dropout visit should be conducted, and the circumstances of the withdrawal or discontinuation have to be recorded in detail in the medical file and the CRF.

If a subject does not return for a scheduled visit, every effort should be made to contact the subject (e.g. by telephone to assess and document treatment compliance, safety, or concomitant medication/therapy) in order to avoid loss-to follow-up or dropout. These efforts have to be documented in the medical file.

Regardless of any decision to modify or discontinue their assigned intervention, study participants should be retained in the trial whenever possible to enable follow-up data collection and prevent missing data. In any circumstance, every effort should be made to document (key) subject outcomes, if possible. The subject has to be requested to return all unused investigational product(s), if applicable, and followed-up regarding any unresolved adverse events.

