19.2.2 Termination by the Investigator

Subjects may also be withdrawn at any time at the discretion of the investigator for safety, behavioral, or administrative reasons, e. g.:

- Occurrence of intolerable events which would constitute an unacceptable high risk for the subject
- Medically indicated e.g. because it is found that inclusion / exclusion criteria were violated
- Continuation is unacceptable because risks outweigh the benefits
- Lack of compliance of the subject
- Significant protocol violations
- Logistical reasons (e.g. subject changes his/her doctor or hospital or moves to another location)

Whenever a subject is withdrawn from the trial, the circumstances of the withdrawal or discontinuation have to be recorded in detail in the CRF and a final examination as scheduled for the termination visit or telephone interview should be conducted.

If a subject does not return for a scheduled visit, every effort should be made to contact the subject.

In any circumstance, every effort should be made to document subject's primary efficacy outcome (PDS total score), if possible. The investigator should inquire about the reason for withdrawal. The subject has to be followed-up regarding any unresolved SAE.

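### Protocol 14.2.2 excludes a patient when the GP leaves the trial, which conflicts with the retention rule in 19.2 and leaves that patient's month-6 PDS-5 unsecured

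*Combined protocol and SAP*

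**What the plan says.** Protocol 14.2.2 has two triggers for exclusion. For an eligibility breach found later, exclusion is optional. For a GP who leaves, it is mandatory: "In the case the family physician terminates the participation in the trial his/her patient will be excluded from the study as well". The section then adds: "Data from patients who drop out of the study after randomization, either through withdrawal or exclusion, are included in an intention-to-treat (ITT) analysis".

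Other sections bear on the same patient:

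- **Protocol 19.2**: "Regardless of any decision to modify or discontinue their assigned intervention, study participants should be retained in the trial whenever possible". It also asks for a final examination when a subject is withdrawn completely.
- **Protocol 19.2.2** lets the investigator withdraw a patient for reasons that include "Logistical reasons (e.g. subject changes his/her doctor or hospital or moves to another location". For these withdrawals it asks for a final examination or telephone interview, and for every effort to record the "primary efficacy outcome (PDS total score), if possible".
- **Protocol 12.6.5** provides a drop-out telephone interview for patients who end the trial early without withdrawing consent. It does so in the paragraph that describes T2.
- **SAP 8.4** analyses patients as randomised, "irrespective of whether they refused or discontinued the treatment, or whether other protocol violations are revealed".
- **SAP 8.1.2 and 8.6** (version 1.4, July 2023) replace the protocol's worst-rank test with a two-sample t-test on the change score and use all available data from drop-outs. No imputation is stated for the principal analysis.

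**The concern.** The GP's departure is not the patient's decision, and it does not prevent measurement. The T1 PDS-5 is a mailed form, with a telephone interview for those who do not return it (SAP 8.1.2), and the interviews are done by central staff (protocol 9.2). A site that applies 14.2.2 literally ends the participation of someone who could still be assessed.

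The stakes come from the trial's aim: "This study aims to describe and compare the real-world effectiveness safety and applicability". When the GP delivers the treatment, a GP who leaves is part of what happens in practice. If such patients have no T1 value, the comparison is restricted to patients whose GP stayed. If GPs leave more often in NET, that restriction differs by arm. This is plausible from the workload. NET asks for 3 hours of training, three 45-minute sessions, a psychologist's call of about 45 minutes and seven calls by practice staff, against three consultations in iTAU. The documents do not state that GPs leave NET more often.

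**Working it through.** **1. The provisions side by side.** The question is whether any provision secures a month-6 PDS-5 for a consenting patient whose GP has left.

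- 19.2 states the goal: "study participants should be retained in the trial whenever possible to enable follow-up data collection and prevent missing data". A site cannot both exclude the patient from the study and retain the patient.
- 19.2.2 covers withdrawal by the investigator. A GP who leaves is not on its list of examples (a patient who changes doctor is), and the effort to obtain the PDS score has no time point.
- 12.6.5 covers patients who stop prematurely, not patients removed because the GP stopped, and it is attached to T2.
- The final examination in 19.2 takes place at exit. An exit score is not the T1 value, which is due at 6 months ± 3 weeks after T0.

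No provision says that T1 is collected after a GP-triggered exclusion, and none says that it is not.

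**2. The planning figure.** Protocol 15.3 uses a 6-point difference, an SD of 17, P = 0.400, two-sided alpha 0.05 and 80% power. Noether's formula gives N = (1.960 + 0.842)² / [12 × 0.25 × (0.40 − 0.50)²] = 7.849 / 0.030 = 261.6, that is 131 per arm. This reproduces the protocol's figure, so 6 points and SD 17 are used below.

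**3. Size if the true benefit is 6 points.** There were 318 randomised patients, taken as 159 per arm under 1:1 allocation. Let q be the share of NET patients excluded because the GP left. This is an assumption, as the documents give no rate. Also assume no benefit in these patients, no T1 value from them and no iTAU loss. Then:

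- ITT effect = 6 × (1 − q)
- observed-case difference = 6
- overstatement = 6q

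**4. Size if there is no true effect.** If the lost NET patients would have been g points worse than the NET patients kept, the t-test is biased toward NET by q × g. The rejection rate follows from the noncentral t distribution with SD 17.

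| q | NET patients lost | ITT effect | Overstatement | Rejection under no effect, g = 5 | g = 10 |
|---|---|---|---|---|---|
| 5% | 8 | 5.7 | 0.3 | 5.2% | 5.8% |
| 10% | 16 | 5.4 | 0.6 | 5.7% | 8.0% |
| 20% | 32 | 4.8 | 1.2 | 7.8% | 16.6% |

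For scale, the standard error of the difference with 159 per arm is 17 × √(2/159) = 1.91 points. The overstatement is therefore about 0.16, 0.31 and 0.63 standard errors.

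**5. What the change of test did.** Under the protocol's worst-rank test, a missing value counted against its arm. In simulation (4,000 runs), power for 6 points is about 89% with 170 per arm and no loss. With 159 per arm and loss in NET only, it is about 55% at q = 5% and 21% at q = 10%. Under the SAP's t-test, the same loss works in favour of NET. The ITT sentence in 14.2.2 was written when every missing value received a rank. It no longer brings a patient without T1 into the principal analysis.

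**6. The sensitivity analyses.** PDS-5 is measured only at T0, T1 and T2. A patient excluded before T1 and not followed further contributes T0 alone. Unless GP withdrawal is modelled, a mixed model or imputation under MAR predicts that patient's outcome largely from NET patients whose GP continued.

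**The case against.** The case on the other side is substantial. The protocol repeatedly asks for outcome data after early termination. A reader might infer that T1 is lost whenever the GP leaves, but the documents do not say so. For the withdrawals in 19.2.2 they explicitly ask for the PDS score. A reader might also infer a contradiction with ITT. There is none in the wording, because 14.2.2 places excluded patients' data in the ITT analysis. The gap is practical: there may be no T1 value to include.

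A further tempting reading is that failures to deliver NET are removed from the NET arm only or mainly. The text does not support it. The rule applies to both arms, and only when the GP ends participation. A GP who misses sessions but stays in creates a protocol violation (15.5), and the patient remains in the ITT analysis. Nor do the pilot results in protocol 5.1 give an exit rate. One reports GPs with time constraints and the other comes from an 8-session version.

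SAP 8.1.2 reports relatively low drop-out, though not by arm or cause. The SAP also plans a drop-out analysis, weighting, mixed models and imputation, and protocol 15.5 has reasons for missing data documented. All of this stands, but these analyses are descriptive or sensitivity analyses, and none requires GP-triggered exclusions to be shown by arm.

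Timing also limits the remedy. Recruitment closed on 31 December 2022, so the last T1 windows (6 months plus 3 weeks) closed by about late July 2023, the month of the SAP. A rewritten rule can recover little of the primary outcome.

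**Conclusion.** The conflict between 14.2.2 and 19.2 is real. With a t-test on available data it can affect the primary comparison, because a randomised, consenting and reachable patient may have no T1 score for a reason unrelated to measurement. The size is unknown, since no GP-withdrawal rate is given. The 0.3, 0.6 and 1.2 points at 5%, 10% and 20% NET loss are illustrations. They rest on four assumptions that all enlarge the result: a 6-point benefit in treated patients, none after the GP leaves, no T1 obtained, and no loss in iTAU. Equal loss with the same kind of patient in both arms would largely remove the bias between arms. If few GPs left, or if T1 was collected anyway, the effect is negligible. The trial's own records can settle this, and the plan should require that they be shown.

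**What to change.** **Protocol.** Reconcile 14.2.2 with 12.6.5, 19.2 and 19.2.2. State that a GP's withdrawal, or an eligibility breach found later, affects at most the assigned intervention and does not end outcome collection. The mailed PDS-5 and the central telephone interview go ahead at the scheduled T1 and T2 times unless the patient withdraws consent.

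**Patients already excluded this way.** Where consent still stands, collect any T2 still due. The planned last visit is 31.12.2023.

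**SAP 8.6.** Add that post-randomisation exclusions are tabulated by arm and reason, with GP withdrawal as its own category and the number with a T1 value shown, and that every T1 or T2 value obtained stays in the ITT analysis.

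**Cost.** A few more mailings and calls by staff already in place, and one table. The protocol change may count as substantial under 20.4, because it bears on the informational value of the results, and would then need an ethics opinion. At this stage the gain is mainly in T2 and in transparent reporting of T1.

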14.3 Quality management

Quality management will be carried out on several levels by the ITC and the regional study centers (RTCs).

To ensure accurate, complete, consistent, and reliable data, the ITC will provide advanced support for documentation and study management in order to ensure high quality during all processes in both treatment arms.

The ITC will independently compare and check data base entries of 10% of patients against completed CRFs.

Photos of the life-line and copies of notes collected at S2 for all patients will be sent by the GP pseudonymously to the ITC who will verify if the intervention has been carried out according to the protocol.

15 Statistical Methods

15.1 Planned Statistical Analyses

15.1.1 Analysis of primary efficacy endpoint

Primary efficacy endpoint is the absolute change in the PDS total severity score from baseline at month 6 ($\Delta_6\text{PDS} := \text{PDS}_{T1} - \text{PDS}_{T0}$). By default, the mode of administration is a self-administered paper-based version. For patients who did not complete and send back the paper-based patient questionnaire (non-responding survivors), the PDS-5 total score will be assessed during the telephone survey T1, scheduled 6 months after randomization.

The null hypothesis

$$H_0: G_{\text{NET}}(x) = G_{\text{iTAU}}(x) \quad \text{and} \quad K_{\text{NET}}(t) = K_{\text{iTAU}}(t) \quad (0 < t \leq T)$$

is that the treatment groups NET and iTAU will not differ with respect to the distributions of the observed outcome measure $\Delta_6\text{PDS}$, whereas $G_i(x)$ is the cumulative probability distribution of the observed change in PDS severity scores at T1 in group i ($i = \text{NET}$ or iTAU), and the distribution of times of death (most likely cause of missingness), whereas $K_i(t)$ is the cumulative distribution of informative event times in group i .

The null hypothesis will be tested using a nonparametric model (Lachin, 1999) which is a modified version of the Wilcoxon-Mann-Whitney U-test and which basically allocates the (tied) worst ranks to all missing values (*worst rank score analysis*). The null hypothesis can be rejected if the two-sided p -value related to the test statistic for the treatment effect is equal to or smaller than the significance level $\alpha=0.05$ (two-sided). Note that the test strategy provided in Lachin (Lachin, 1999) is tailored to a particular alternative hypothesis – i.e.,

- NET will either be superior to iTAU in terms of absolute change in PDS severity scores from baseline at T1, but with no impact on survival,
- NET will be superior to iTAU in terms of survival, but with no impact on the absolute

- change in PDS severity scores from baseline at T1,
- or NET will be superior to iTAU for both the absolute change in PDS severity scores from baseline at T1 and survival.

Explanation of the allocation of the worst ranks to all missing values: If the PDS total severity scores are not informative for future death events, the worst rank replacement will simply lead to a power loss and no inflation in the type I error rate. Should the PDS total severity scores be informative for future death events, the worst rank replacement will result in an unbiased test (as shown by (Lachin, 1999)) of a particular alternative.

The principal analysis will be performed according to the intention-to-treat (ITT) principle, and unadjusted for screening or baseline covariates or site. The significance level is set to $\alpha = 5\%$ (two-sided).

Missings prior to the time of the follow-up measurement will occur because of an informative, disease-related event (e.g. death, morbidity) and for other reasons (e.g. non-responders at follow-up measurements T1, T2, loss to follow-up, consent withdrawn). To address the impact of several missingness mechanisms (MAR; MNAR) sensitivity analyses will be performed, e.g. mixed effect models assuming MAR (“all observed data approach”) using the whole observed PDS profile of the surviving patient; multiple imputations techniques; or even complete case analyses using ANCOVA (absolute change score as response variable, treatment group as covariate, adjusting for the baseline score value) for responding survivors until T1.

Moreover, we plan sensitivity analyses in the per protocol population, using linear mixed effects models to explore the role of covariates (e.g. age and gender) and to address the Behrens- Fisher problem.

Further methodological details will be provided in the SAP to be written in a blinded fashion.

